*** 3. Describe any direct benefits to participants, if any.**

Note:

Payments or incentives (including credit) should be discussed in section 6.9.a.

There are no direct benefits of this research. However, participants may enjoy being part of the study and discussing the topics with others.

*** 4. Will any individual results of the research or procedures/tests completed, be provided back to the participant?**

No

*** 5. Describe the benefits of the research to society, if any.**

The information provided in this research will strengthen the surveys and procedures for Component B-- the evaluation of the prevention program curriculum. Results will be valuable to help keep youth healthy and to prevent the CSEC.

*** 6. Describe all risks to the participant including a breach of confidentiality, if applicable. What will be done to minimize the risk(s)? If there are no known risks, this should be stated.**

The risks of this study are minimal. Participants may feel sad or anxious or award when we discuss sensitive topics however, none will be asked about their personal experiences. Instead, this study is intended to obtain perceptions about the issues in Component B (e.g., perceptions of CSEC in their school, school norms regarding the acceptability of CSEC; Focus group data) and to see if the surveys make sense (e.g., "does this question make sense and if not why?", cognitive interviews). A resource page for services in the Des Moines area related to, for example, sex trafficking, sexual violence, homelessness, physical/domestic violence etc... will be provided to each participant. (see Resource Sheet, attached).

Information has been included at the lead in to the FGs indicating that we will not be asking about personal experiences and asking that participants not provide information on personal experiences. If information is provided that requires mandatory reporting the following steps will be made:

1. the researcher will contact the PI
2. the PI will report the incident to the proper authorities (most likely Iowa Department of Public Health and/or law enforcement);
3. PI will report incident to IRB

An additional risk is that there is no guarantee that a member of a focus group won't share what is said as part of the focus group. However, we will stress that all information discussed in the FG is confidential and stress the importance of maintaining that confidentiality after the FG is over. Language to this effect has been included in all FG consent forms/assent forms. Because we are not asking about personal experiences, there are no negative consequences or known risks if a breach of confidentiality should occur.

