*** 7. Describe your access to the population that will allow recruitment of the necessary number of participants. For example, if you are an employee of an organization that will allow for the research to occur, are the instructor of the classroom in which the research will take place, or you have a professional/personal relationship with someone in the targeted population, etc., describe that in your response.**

The PIs (Drs. [name] and [name]) have a professional relationship with the DMPS administration including the superintendent (see Letter of support), Executive Director of Student Services, [name], Director of School Climate Transformation, [name], Director of High Schools, and [name], Executive Director of Data and Assessment. We are working directly with [name] (DMPS Educational Liaison Consultant), and [name] (DMPS SUCCESS Supervisor). This group will work with us to coordinate recruitment.

*** 8. Describe the process that will be followed, facilities available, or locations that will be used during the conduct of research to protect the privacy of participants, if applicable. In this**

question, privacy refers to procedures such as how a participant will complete a sensitive research questionnaire in private without having the possibility of someone reading their responses over their shoulder or possibly having someone overhear responses during an interview.

We will be collecting focus group discussions (FGD) with school personnel (n=60) and youth (n=80) and cognitive interviews with youth (n=20). All FGD will include groups of ~10 people and occur in a private space in a DMPS library or empty classroom. Responses from FG participants will be anonymized (no names associated with responses). All FGD participants will be asked to maintain privacy of all information shared within the discussion--however, there is no guarantee that FG participants will not share information outside the discussion (and this is in the consent/assent forms). Cognitive interviews (n=20) will occur one-on-one (between participant and research staff member trained by [name]). These will occur in a private room in a DMPS library, office or an empty classroom. Cognitive interview data/transcripts will be de-identified by a member of the research team.

In terms of youth: the first from each school who express interest, meet inclusion criteria, and have parental consent will be included.

Exclusion Criteria

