After the initial item pools for the survey instruments have been created following focus groups, research advisory input, and an updated and extensive literature review, the researchers will conduct cognitive interviews with students (N=20 across all 8 high schools). These will be used: to ensure that students understand the survey questions, to determine if questions need modifying to be more salient/relevant to the age group and local context, to ensure that the response options are meaningful, etc. More specifically, participants will be asked to read each question and response options aloud. We will ask probing questions such as, tell me in your own words what this means, does this question make sense and if not why, how could we make this question better, etc (see Cognitive Interview Script_Youth, attached).

[The measures that are to be used in the cognitive interview procedures will be submitted via a change request form once they are confirmed through the FG data analyses, lit review, and consultation with the research advisory board].

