*** 7.c. Describe how often the data will be reviewed.**

The research team will be monitoring the data provided by participants for as the data are being collected (during FG or interviews). The PI will be contacted if any problems are detected (e.g., personal disclosures; individuals showing up without proper consent/parental consent/assent; upset at the questions or emotional distress).

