Aim 2a. Power analyses to support the sample size for the effectiveness analyses for our primary, secondary, and intermediary outcomes (see Figure 1) were conducted using G-Power 3.1. Power was set to .80 and $\alpha=.05$. Component A of the study will provide incidence rates which will be used to recalculate power prior to the implementation of Component B. For the purposes of this proposal, we calculated the MDES based on the proposed sample size. For the primary outcome of CSEC perpetration, there are no reliable incidence estimates in the literature on which to draw. With a sample size of 7,241 students enrolled, assuming conservative minimum incidence rates of CSEC perpetration of 1% to 5% (although we hypothesize it will be higher), we have power to detect an MDES difference between conditions, odds ratio (OR)=.49 to .75, respectively. Similarly, for secondary outcomes of CSEC victimization, we estimated a range of incidence rates from a conservation 5% to 50%+ based on literature discussed following for other types of victimization^{96, 132, 133} as well as rates of CSEC youth at increased risk (e.g., system involved, homeless)¹⁸⁻²⁰, which will be present in our sample based on DMPS data, we have the power to detect an MDES difference between conditions, odds ratio (OR)=.75 to .88, respectively. For secondary outcomes of TDV/SV perpetration and victimization, given past 12- months incidence rates¹³² (from nationally representative data from youth) of 63% for perpetration (of any type of TDV) and 69% for victimization (of any type of TDV), we have power to detect an MDES difference between conditions, odds ratio (OR)=.88 to .89. For sub-types of TDV (past 12-month incidence rates: physical victimization: 18%; sexual victimization: 18%; psychological victimization: 66%; physical perpetration: 12%; sexual perpetration: 12%; psychological perpetration: 62%)¹³², we have power to detect an MDES difference between conditions, odds ratio (OR)=.83 to .89, respectively. For the secondary outcome CSEC bystander action and opportunity and intermediary outcomes (i.e., knowledge, valuing of self and others, healthy relationship skills, bystander efficacy, perceptions of school social norms, prevention conversations with school personnel), the ANCOVA routine suggested power (.80) to detect a small difference between groups (MDES $d=.06$).

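### The protocol's statement that a confidentiality breach carries no risk conflicts with its own disclosure and reporting provisions, and the described lead-in covers only focus groups and one's own experiences

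*Protocol*

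**What the plan says.** Protocol, Benefits and Risks, item 6, asks for all risks, including breach of confidentiality. The answer makes four statements that bear on this point.

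- On prevention: "Information has been included at the lead in to the FGs indicating that we will not be asking about personal experiences". Participants are also asked not to volunteer such information. This step is described for the focus groups.
- On what follows a disclosure: "If information is provided that requires mandatory reporting the following steps will be made". The steps run from the researcher to the PI, then to the authorities (possibly law enforcement) and the IRB.
- On retelling: "An additional risk is that there is no guarantee that a member of a focus group won't share what is said".
- On the result: "Because we are not asking about personal experiences, there are no negative consequences or known risks if a breach of confidentiality should occur".

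Data Monitoring & Sharing, item 7.c, covers both focus groups and interviews: "The PI will be contacted if any problems are detected (e.g., personal disclosures". Item 7.d adds that the IRB is notified when mandatory reporting is required.

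On the setting, Inclusion Criteria, item 8, states: "All FGD will include groups of ~10 people". Purpose, Methods & Procedures, item 3, plans roughly one youth group per school and has youth discuss commercial sexual exploitation of children (CSEC) as they see it in their own school. For the cognitive interviews, the same item states that "participants will be asked to read each question and response options aloud". Both kinds of session are audio-recorded (Research Methodology and Data Sources, item 1.a).

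The SAP, Power Analyses, Aim 2a, gives planning rates for CSEC victimization in the later evaluation: "we estimated a range of incidence rates from a conservation 5% to 50" percent, with the upper end left open.

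**The concern.** The no-risk conclusion is drawn from what the researchers will ask. Harm from a breach depends on what participants say. The protocol itself expects that some may say things they were not asked, because it plans to detect such disclosures and, where required, to report them. A risk assessment that assumes they do not occur is incomplete on the very question the item poses.

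Two practical gaps follow from the protocol text. First, the request not to share is not described for the cognitive interviews. There, a youth reads sensitive survey items and their response options aloud, one-on-one with a staff member and on a recording, so giving one's own answer while reading is foreseeable. Second, the request as described concerns one's own experiences. In a group drawn from one school and discussing that school, a participant could describe a recognisable classmate or staff member without departing from the instruction.

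At stake is the accuracy of the risk information behind a study that enrols minors on a sensitive subject, and the completeness of an inexpensive preventive step.

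**Working it through.** **Step 1: set the passages side by side.** The argument in Benefits and Risks, item 6, is: personal experiences are not asked about, so nothing harmful can come out in a breach. The missing premise is that nothing personal is volunteered. Three places in the protocol deny that premise:

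| Place | What it assumes |
|---|---|
| Benefits and Risks, item 6, reporting steps | Reportable information may be given |
| Data Monitoring & Sharing, item 7.c | Personal disclosures may occur in groups or interviews |
| Data Monitoring & Sharing, item 7.d | Mandatory reporting may be required |

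Item 6 also conflicts with itself. It classes retelling by group members as a risk, then says that a breach has no known risk. A mandatory report is not itself a breach by a group member. It matters here because it shows that the protocol foresees content serious enough to have consequences if repeated.

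**Step 2: scope of the lead-in.** Groups: described, for one's own experiences. Interviews: the protocol says youth will not be asked about personal experiences, but describes no request that they refrain from offering them. Other identifiable people: not mentioned for either.

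**Step 3: reproduce the plan's count.** 10 youth per school × 8 schools = 80, the stated number of focus group youth. A further 20 youth have cognitive interviews.

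**Step 4: context on how often affected youth would be present.** The documents state no such figure. Assume that participants are independent and have the SAP's CSEC victimization rate p. For a group of 10, P(at least one affected) = 1 − (1 − p)^10.

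- p = 5%: 1 − 0.95^10 = 0.401, or 40%.
- p = 50%: 1 − 0.50^10 = 0.999, or 99.9%.
- Even odds are reached at p = 1 − 0.5^(1/10) = 6.7%.
- With 8 to 12 per group, since 10 is approximate, the 5% result runs from 34% to 46%.

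For the 20 interviewees:

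- Expected number affected: 20 × 0.05 = 1 to 20 × 0.50 = 10.
- P(at least one affected) at 5%: 1 − 0.95^20 = 0.642, or 64%.
- Any single interview: 5% to 50%.

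For all 8 youth groups to include an affected youth:

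- p = 5%: 0.401^8 = 0.0007, or 0.07%.
- p = 50%: 0.999^8 = 0.992, or 99.2%.

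These are chances that an affected youth is present. No document gives a rate of disclosure, so the chance or cost of a harmful breach cannot be computed.

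**The case against.** The strongest reply is that planning for an unsolicited event is ordinary prudence, and that the protocol has many protections: a resource sheet, counselors on site, at least two researchers per focus group, debriefing, immediate contact with the PI, a Certificate of Confidentiality, de-identification, deletion of recordings, and participant lists kept apart from data. The focus group consent and assent forms are said to warn that other members may repeat what they hear. The disputed sentence closes a paragraph on that route, which does not exist in a one-on-one interview. The interview probes test comprehension and do not ask for the youth's own answers.

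Most of this stands as mitigation. It does not rescue the sentence, because reducing a risk is different from having none, and the protections presuppose that something could go wrong. In the interviews the retelling route is indeed absent, but the recording remains.

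Four stronger readings are tempting and are not supported.

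- *That affected youth are likely in every session.* At the SAP's low rate a group of 10 is below even odds, a single interview stands at 5%, and the chance that all eight groups include an affected youth is 0.07%.
- *That the SAP contradicts the protocol.* Its rates are inputs to a detectable-effect calculation for Component B. The victimization range is borrowed partly from other kinds of victimization and from higher-risk youth.
- *That families would be told a breach has no consequence.* Item 6 is an answer to the IRB. The coordinator does go over risks with parents by phone (Informed Consent Process, item 1), but the consent and assent forms are separate attachments that are not shown.
- *That the interviews lack the lead-in.* The interview script is also an attachment not shown. One can say only that the protocol text describes none.

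**Conclusion.** The risk statement in Benefits and Risks, item 6, is wrong as written. Its conclusion does not follow from its reason, and it conflicts with the reporting steps and the retelling risk in the same answer and with items 7.c and 7.d of Data Monitoring & Sharing. This rests on the text alone and needs no assumed rate.

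The limited scope of the lead-in is a smaller point: a cheap improvement, conditional on what the unseen script and forms contain.

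The size is known only as presence: 40% to 99.9% per group of 10, and 1 to 10 expected among 20 interviewees. This assumes independence and that Phase I volunteers resemble the population behind the SAP's 5% to 50% range. Volunteers may differ in either direction. The figures show that the issue is not remote. They do not show that disclosure is probable, and the case for the change does not depend on them.

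**What to change.** 1. Reconcile item 6 with items 7.c and 7.d. Replace the no-consequence sentence with a statement that unsolicited disclosures are possible, could become known through other group members or the recording, and may have to be reported.
2. Check that the risk text in the consent and assent forms says the same, and amend it if it does not.
3. Confirm that the cognitive interview script carries the lead-in, or add it, including that youth need not give their own answers while reading items aloud.
4. In all sessions, widen the lead-in to ask participants not to name or describe identifiable students or staff.
5. Leave the reporting chain unchanged.

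The cost is one edited paragraph and a few lines in scripts and forms. The protocol already plans a change request for the interview measures, with consent and other edits to follow (Purpose, Methods & Procedures, item 3; Questionnaires, Surveys, and Testing Instruments), so the changes can go in with it. A franker risk statement might lower uptake slightly.

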*** 7. Does this research involve procedures, equipment or tests that could reasonably result in an incidental finding?**

No

*** 8. Describe the availability of medical or psychological resources that participants might require as a consequence of the research and/or in the case of incidental findings, if applicable.**

Data will be collected within the DMPS school system (library, gym, office, empty classroom). There are counselors on site at each school, as well as trained personnel (teachers, special education instructors, etc...). In addition, we will provide all participants with a list of resources available within the Des Moines community.

Compensation/Incentives and/or Cost for Participation

*** 9. Will compensation or incentives (including money, gift certificates, extra credit, books, t-shirts, etc.) be provided to participants?**

Yes

*** 9.a. Describe the amount and form of compensation. If providing research or course credit, please describe the alternate activity that will be available for students who choose not to participate in the project and still want to receive credit. If a lottery/raffle is offered, please describe the odds of winning and when the winning participant(s) is expected to be notified.**

If the project is supported through a form of funding, including department, internal, or start-up funds UNL accounting requirements must also be met when documenting receipt of participant payments. Describe how UNL accounting requirements will be met, specifically when handling payment receipts that include individual identifying information.

Each person will be provided a \$25 gift card; they will sign a form indicating they received the gift card (see attached). These receipts will not be attached to any of the collected data.

*** 10. Will the research require the participant to pay for any aspects of the study or cost for participation, including cost for travel and transport to and from the study site?**

No

Informed Consent Process

*** 1. Describe how informed consent/assent will be obtained and the process that will be followed to ensure the participant understands the information presented. (Upload age appropriate consent/assent forms, if applicable, on page nine.)**

YOUTH:

1. Project coordinator will go over the key parts of the study (purpose, risks, procedures) with the parent (while on the phone) to make sure they understand, answer all questions, and then email or text a link to the parental consent form.
2. Once the parental consent form is obtained, the PC will contact the youth, schedule the FG or cogn. interview, and send a link to the youth assent form via email or text. Phone number of PI and PC are included on the form with instructions to contact if they have questions.

SCHOOL PERSONNEL:

1. Project coordinator will send (via text or email) the consent form to school personnel.

*** 2. Describe the person(s) who will obtain participant consent/assent.**

The project coordinator will obtain consent, parental consent, and youth assent.

*** 3. Describe who will provide consent/assent. If you have identified the inclusion of either child or adult wards or persons with a legally authorized representative (LAR) within section 3.2 of the protocol, describe the process that will be followed to ensure the LAR is providing the consent for the participant.**

School Personnel (18+) provide consent for themselves (see attached).

Parents/guardians will provide parental informed consent for their youth. On the consent form, the parent/guardian confirms that they are legally responsible for the youth they are consenting (see attached). After parental consent is obtained, youth will be contacted by PC, questions answered about the study, and then a link to the assent will be emailed or texted.

*** 4. Describe the waiting period, if any, between when the potential participant will be informed of the study and when consent will be obtained. If multiple data collection points are included within the project, describe the amount of time between each period.**

SCHOOL PERSONNEL: All school personnel interested in the project will contact the Project Coordinator (PC) who will provide more information about the study and schedule the FG if s/he wants to participate. At that time, a link to the informed consent

form will be emailed (or texted) to the person to complete and submit. (no waiting period).

*If consent has not been received, the PC will remind of this and send a new link when the PC calls for the reminder of the scheduled FG.

*The PC will provide the researchers leading the FG a list of people who have provided consent and who are scheduled for that FG

YOUTH: All youth interested in the project will contact the Project Coordinator (PC) who will provide more information about the study and determine whether the youth is interested in the FG or cognitive interview. The youth will provide contact information for his/her parent/guardian. The PC will then contact the parent/guardian and explain the study and then email or text a link to the parental consent form if they are willing to allow their youth to participate. Once that has been completed, the PC will contact the youth, schedule data collection, and then send the link (text or email) to the youth to obtain youth assent. (minimal waiting period)

*Cognitive interviews & FG are scheduled after receiving parental consent. The PC will provide the researchers leading the FG a list of youth who have received parental consent and provided assent and who are scheduled for that FG. Anyone who arrives without the required documentation completed will be asked to leave.

*The PC will remind the youth about the assent form when s/he calls to remind about the scheduled interview/FG. If the youth still does not complete the assent by the day prior to the interview, it will be cancelled.

